4. POPULATIONS (ANALYSIS SETS) FOR ANALYSIS

The following sets will be used for analyses.

Table 4: Analysis sets

Analysis Sets	Description	
Enrolled	All participants who signed the ICF	
Randomized	All participants who were randomized in the study	
Full Analysis Set (FAS)	All randomized participants who received at least 1	
	(partial or complete) dose of study intervention	
Rescue Analysis Set	All participants in the FAS who met rescue criteria (as	
	determined by the IWRS) and received at least one	
	(partial or complete) dose of study intervention at or	
	after Week 16. This includes both participants	
	randomized to placebo and participants randomized to	
	one of the guselkumab groups who were assigned sham	
	rescue treatment.	

Analysis Sets	Description	
Week 12 Clinical Responder Analysis Set	All participants in the FAS who met Clinical Response	
	Criteria at Week 12 as defined in Section 5.4.1.1 and	
	received at least 1 (partial or complete) dose of study	
	intervention after Week 12	
Safety	All randomized participants who received at least 1	
	(partial or complete) dose of study intervention	
Pharmacokinetics (PK) Analysis Set	All participants who received at least 1 (partial or	
	complete) dose of guselkumab and have at least 1 valid	
	blood sample drawn for PK analysis after their first dose	
	of guselkumab	
Immunogenicity Analysis Set	All participants who received at least 1 (partial or	
	complete) dose of guselkumab and have appropriate	
	serum samples for detection of antibodies to	
	guselkumab after their first dose of guselkumab	

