5.1.1. Visit Windows

Unless otherwise specified, actual scheduled visits will be used for over time summaries and listings with no visit windows applied. Early Discontinuation (ED) and unscheduled efficacy visits will be slotted to scheduled visits according to the following mapping rules:

- 1. Assign a visit number to ED or unscheduled visit based on the visit day according to Table 6.1 and Table 6.2.
- 2. If the ED or unscheduled visit falls in the window of a scheduled visit for which there is no data recorded, assign the scheduled visit number to the ED or unscheduled visit. If there is data recorded for the scheduled visit, those data will be used in lieu of the ED or unscheduled visit data.

Table 5.1: Visit windows for analysis of Mayo score, endoscopy score and histology assessment

Parameter	Time interval (label on output)	Time interval (Day)*	Target time point (Day)
Partial Mayo Score	Week 4	16-43	29
	Week 8	44-71	57
	Week 12	72-99	85
	Week 16	100-127	113
	Week 20	128-155	141
	Week 24	156-183	169
	Week 28	184-211	197
	Week 32	212-239	225
	Week 36	240-267	253
	Week 40	268-295	281

CONFIDENTIAL – FOIA Exemptions Apply in U.S.

11

	Week 44	296-323	309
	Week 48	324-351	337
Endoscopy subscore, full			
Mayo score including	Week 12	57-113	85
modified Mayo score			
	Week 24	141-197	169
	Week 48	309-365	337
Histology assessment	Week 12	57-113	85
	Week 48	309-365	337

^{*} Relative to Study Day 1

Table 6.2: Visit windows for analysis of IBDQ, PROMIS-29, UC-PRO/SS, fecal calprotectin, CRP

D	Time interval	Time interval	Target time point
Parameter	(label on output)	(Day)*	(Day)
IBDQ, PROMIS-29	Week 12	57-113	85
	Week 24	141-197	169
	Week 48	309-365	337
UC-PRO/SS	Week 4	16-43	29
	Week 8	44-71	57
	Week 12	72-99	85
	Week 16	100-127	113
	Week 20	128-155	141
	Week 24	156-183	169
	Week 28	184-211	197
	Week 32	212-239	225
	Week 36	240-267	253
	Week 40	268-295	281
	Week 44	296-323	309
	Week 48	324-351	337
Fecal calprotectin	Week 4	16-56	29
•	Week 12	57-113	85
	Week 24	141-197	169
	Week 48	309-365	337
CRP	Week 4	16-43	29
	Week 8	44-71	57
	Week 12	72-99	85
	Week 16	100-127	113
	Week 20	128-155	141
	Week 24	156-196	169
	Week 32	197-253	225
	Week 48	309-365	337

^{*} Relative to Study Day 1

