2. A prohibited change in medications for UC (as	treated as an unfavorable outcome
defined in Appendix 14)	
3. Discontinuation from study intervention due to lack	
of efficacy or an adverse event (AE) of UC worsening	
4. Meeting rescue criteria (as determined by the IWRS)	
(Note: Since rescue criteria are assessed at Week 16	
for all participants, this ICE is not applicable for the	
primary endpoint or any of the key secondary Week 12	
endpoints)	
5. Discontinuation of study intervention due to	Treatment policy strategy: Observed values will be
COVID-19 related reasons (excluding COVID-19	used if available
infection) or regional crisis	
6. Discontinuation of study intervention due to reasons	Composite strategy: Occurrence of these ICEs will be
other than ICEs 3 or 5 as described above	treated as an unfavorable outcome

The composite strategy assesses the treatment effect not only based on the variable measurements, but also on ICEs. This estimand acknowledges that having an ICE in categories 1-4 and 6 is an unfavorable outcome. For participants experiencing an ICE in category 5, the treatment policy strategy considers the occurrence of ICE category 5 as irrelevant in defining the treatment effect.

v) Population-level summary: Difference in proportions of participants who achieved the binary response at Week 12 as defined in the variable attribute above between the combined guselkumab group and the placebo group.

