5.4.1.3. Supplementary Estimands for Secondary Endpoints

5.4.1.3.1. Treatment policy for discontinuations (Estimand 5)

Supplementary estimands (Estimand 5 for secondary endpoints) handle all treatment discontinuation ICEs, i.e. ICEs 3, 5 and 6 in Table 6, by the treatment policy strategy. ICEs 1, 2 and 4 in Table 6 continue to be handled by the composite strategy. This leads to the variable definitions given in Table 9.

Table 9: Variable Attributes of Secondary Endpoints for supplementary estimand

Endpoint	Variable attribute
Symptomatic remission Week 12	A binary response variable (response/nonresponse) where response is defined as achieving a stool frequency subscore of 0 or 1 and not increased from baseline, and a rectal bleeding subscore of 0 at Week 12 and none of the ICEs in categories 1, 2 and 4 outlined in Table 6 has occurred prior to the Week 12 visit
Endoscopic improvement Week 12	A binary response variable (response/nonresponse) where response is defined as achieving an endoscopy subscore of 0 or 1 with no friability present on the endoscopy at Week 12, where none of the ICEs in categories 1, 2 and 4 outlined in Table 6 has occurred prior to the Week 12 visit
Clinical response Week 12	A binary response variable (response/nonresponse) where response is defined as achieving a decrease from induction baseline in the modified Mayo score by $\geq 30\%$ and ≥ 2 points, with either a ≥ 1 -point decrease from baseline in the rectal bleeding subscore or a rectal bleeding subscore of 0 or 1 at Week 12, where none of the ICEs in categories 1, 2 and 4 outlined in Table 6 has occurred prior to the Week 12 visit
Histologic- endoscopic mucosal improvement Week 12	A binary response variable (response/nonresponse) where response is defined as a combination of histologic improvement [neutrophil infiltration in <5% of crypts, no crypt destruction, and no erosions, ulcerations or granulation tissue according to the Geboes grading system (Appendix 11)] and endoscopic improvement [endoscopy subscore of 0 or 1 with no friability present] at Week 12, where none of the ICEs in categories 1, 2 and 4 outlined in Table 6 has occurred prior to the Week 12 visit

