5.5.4. Analysis Methods

Unless otherwise specified, the exploratory endpoints listed and defined in Sections 5.5.1 to 5.5.3 will be analyzed based on the FAS according to the randomized intervention group, regardless of the intervention actually received.

No confirmatory tests will be performed on exploratory endpoints, regardless of the significance for primary and secondary endpoints. Nominal p-values will be presented without adjustments for multiple comparisons.

Descriptive statistics (mean, median, SD, IQ range, minimum, and maximum) will be used to summarize continuous variables. Counts and percentages will be used to summarize categorical variables. Graphical data displays (e.g., line plots) may also be used to summarize the data.

Binary endpoints

The main estimand approach and the estimator used for the secondary endpoints (Section 5.4.1.2) will be used to summarize and compare binary endpoints. Intercurrent events will be handled as specified in Table 6.

The handling of ICEs specified in Section 5.4.1.2 will be applied to each of the above binary endpoints. Participants with ICEs in categories 1-4 and 6 will be considered not to have achieved the binary endpoint, while observed values will be used for participants experiencing an ICE in category 5.

Participants with any missing data for an endpoint after application of ICE handling rules will be imputed as not having achieved the associated binary endpoint. Binary endpoints will be summarized with the number and percentage of participants who achieve the endpoint by intervention group. To compare the proportion of participants achieving the endpoints, MH tests stratified by the ADT-IR status (Yes/No), and Mayo endoscopy subscore at baseline (moderate [2] or severe [3]) will be provided. In case of rare events, Fisher's exact test will be used for intervention comparisons.

Continuous endpoints

For continuous endpoints, handling rules for ICEs as defined in Table 6:

- Composite strategy (categories 1-4 and 6): Baseline values will be assigned from the point of ICE onward
- Treatment policy strategy (category 5): Observed values will be used, if available

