5.5.4.1. Subgroup Analyses

Subgroup analyses for subgroups defined by the stratification variables (ADT-IR yes/no, baseline endoscopic subscore moderate [2]/severe [3]) will be performed using the FAS for the following exploratory endpoints (all as defined in Section 5.5.1.2):

- Histologic improvement
- Histologic remission
- Combination of histologic remission and endoscopic improvement

The following analysis approach will be applied:

- The consistency of intervention effect will be evaluated, using the main estimand and handling missing data by the rules specified in Section 5.4.2.1.
- The adjusted treatment difference of the combined guselkumab SC group vs. the placebo SC group and the associated p-values and 95% confidence intervals will be provided. The treatment differences, p-values and confidence intervals will be obtained from a MH test stratified by the remaining stratification factor.

In addition, descriptive analyses will be performed for the rescue analysis set for the following endpoints:

- Clinical remission (primary definition as given in Table 10 only) at Week 48
- Symptomatic remission over time
- Change from baseline in partial Mayo score over time
- 8-week corticosteroid-free clinical remission at Week 48: Defined as being in clinical remission at Week 48 and not having received corticosteroids between Week 40 and Week 48
- Change from baseline in CRP concentration [mg/L] over time
- Change from baseline in fecal calprotectin concentration [mg/kg] over time

Descriptive analyses will be performed for the Week 12 Clinical Responder Analysis Set for the following endpoints:

- Clinical remission at Week 24 and at Week 48
- Symptomatic remission over time
- Deep symptomatic remission at Week 24 and at Week 48
- Mayo stool frequency subscore of 0 or 1 over time
- Mayo rectal bleeding subscore of 0 over time
- Clinical response at Week 24 and at Week 48
- Clinical response through Week 48 (at both Week 24 and Week 48)
- Endoscopic normalization at Week 24 and at Week 48
- Endoscopic improvement at Week 24 and at Week 48
- Change from baseline in CRP concentration [mg/L] over time
- Change from baseline in fecal calprotectin concentration [mg/kg] over time
- Deep symptomatic remission (Mayo stool frequency subscore of 0 and Mayo at rectal bleeding subscore of 0) over time

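### In the Rescue Analysis Set, meeting rescue criteria is both the condition for entry and a failure event (ICE 4), so every efficacy result after Week 16 is fixed in advance

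*SAP*

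**What the plan says.** SAP Table 4 defines the Rescue Analysis Set as "All participants in the FAS who met rescue criteria (as" determined by the IWRS) and who were dosed at or after Week 16. It includes placebo participants rescued with guselkumab and guselkumab participants given sham rescue.

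SAP Table 6 lists as an intercurrent event "4. Meeting rescue criteria (as determined by the IWRS"), assigns it the composite strategy, and notes that the assessment takes place at Week 16.

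SAP Section 5.5.4 sets the rules for the exploratory endpoints:

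- Binary: "The handling of ICEs specified in Section 5.4.1.2 will be applied to each of the above binary endpoints", and "Participants with ICEs in categories 1-4 and 6 will be considered not to have achieved the binary endpoint".
- Continuous: "Composite strategy (categories 1-4 and 6): Baseline values will be assigned from the point of ICE onward".

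Section 5.5.4.1, a subsection of 5.5.4, then says: "In addition, descriptive analyses will be performed for the rescue analysis set for the following endpoints". The six endpoints are clinical remission at Week 48, symptomatic remission over time, change in partial Mayo score over time, 8-week corticosteroid-free clinical remission at Week 48, and change in CRP and in fecal calprotectin over time. It does not say how ICE 4 is treated for them.

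**The concern.** The event that admits a participant to the set is also the event that makes that participant a non-responder, or returns the value to baseline. Everyone in the set therefore has the same imputed outcome after rescue.

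The tables would then fail at the one thing they are for. The SAP version history says the set was added because the number of rescued participants warranted it. Protocol Section 4.2 justifies keeping sham-rescued guselkumab participants on drug by the possibility of a delayed response. Under the stated rules the output can show neither a response to rescue in placebo participants nor a late response in guselkumab participants. The set's other planned uses are disposition, baseline and medication summaries, so no other planned efficacy output would fill the gap.

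**Working it through.** The plan gives no figure to reproduce here. The check is logical, followed by a count.

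**Step 1: membership implies ICE 4.** Table 4 requires rescue criteria met per the IWRS plus a dose at or after Week 16. Table 6 defines ICE 4 as rescue criteria met per the IWRS. The set is thus a subset of the participants with ICE 4, and 100% of its members have it.

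**Step 2: the 5.5.4 rules reach all six endpoints.** Section 5.5.4 governs the endpoints of Sections 5.5.1 to 5.5.3 unless otherwise specified. Clinical remission, symptomatic remission and partial Mayo change are in 5.5.1.1, 8-week corticosteroid-free remission is in 5.5.1.3, and CRP and fecal calprotectin are in 5.5.3.

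**Step 3: timing.** ICE 4 occurs at Week 16. The binary variable definitions (SAP Tables 7 and 8) count ICEs that occurred before the visit, so binary results are forced at visits after Week 16. The continuous rule runs from the ICE onward, so those results are forced at Week 16 and later.

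**Step 4: count the visits.** Schedules come from SAP Table 5.1 and from Table 6.2 ("Visit windows for analysis of IBDQ, PROMIS-29, UC-PRO/SS, fecal calprotectin, CRP"). Two readings are assumed: that *over time* means every scheduled post-baseline visit through Week 48, and that symptomatic remission follows the partial Mayo schedule.

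| Endpoint | Visits | Fixed | Value forced |
|---|---|---|---|
| Clinical remission, Week 48 | 1 | 1 | 0/n |
| 8-week corticosteroid-free clinical remission, Week 48 | 1 | 1 | 0/n |
| Symptomatic remission | 12 (Weeks 4 to 48, every 4 weeks) | 8 (Weeks 20 to 48) | 0% |
| Change in partial Mayo | 12 (same) | 9 (Weeks 16 to 48) | mean 0, SD 0 |
| Change in CRP | 8 (Weeks 4, 8, 12, 16, 20, 24, 32, 48) | 5 (Weeks 16, 20, 24, 32, 48) | mean 0, SD 0 |
| Change in fecal calprotectin | 4 (Weeks 4, 12, 24, 48) | 2 (Weeks 24, 48) | mean 0, SD 0 |
| **Total** | **38** | **26** | |

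Fixed: 1 + 1 + 8 = 10 binary and 9 + 5 + 2 = 16 continuous; 26/38 = 68.4%. The remaining 12 are the Week 4 to 12 results and symptomatic remission at Week 16.

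**Step 5: sensitivity to Week 16.** If the Week 16 partial Mayo and CRP values are taken as preceding the ICE, the count is 26 − 2 = 24 (63.2%). If symptomatic remission at Week 16 is also forced, it is 26 + 1 = 27 (71.1%). Every visit after Week 16 is fixed on any of these readings.

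**Step 6: numerical confirmation.** With made-up data (60 rescued participants, assumed true post-rescue response of 10%, 30%, 60% or 90%), the rules returned 0% response after Week 16 and a mean change of 0.0 in partial Mayo from Week 16 in all four cases.

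**The case against.** The best counter-argument is that the rules were never meant to carry over. For the stratification-factor subgroups, Section 5.5.4.1 expressly names the main estimand; for the rescue set it says only that the analyses are descriptive. The opening of 5.5.4 is framed around the FAS, and the endpoint definitions that 5.5.4.1 cites carry no ICE clause. On that view the plan leaves a rule unstated, and observed data were probably intended.

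That intention is plausible, but the text does not support the reading. Section 5.5.4.1 sits within 5.5.4 and changes only the analysis set. Section 5.5.4 uses the main estimand to summarize the binary endpoints as well as to compare them, so calling an analysis descriptive removes the test and leaves the endpoint derivation in place. If the objection were accepted, the rule would be undefined, including whether ICEs 1 to 3 and 6 still count as failure, and the same sentence would be needed.

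Several lesser points do stand. The status of the Week 16 assessment is unclear, because rescue is determined from that visit's own partial Mayo score; hence the range of 24 to 27. A participant without a baseline value has a missing change, not a zero, and drops out of the summary. Estimand 5 retains the composite handling ("ICEs 1, 2 and 4 in Table 6 continue to be handled by the composite strategy"), but it concerns the secondary endpoints; it shows only that it supplies no alternative rule. A table of zeros would also be recognized at once, so the realistic risk is an undocumented choice by the programmer and not a false conclusion.

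**Conclusion.** The concern holds: the plan is wrong as written for this set. A stated rule, applied literally, forces 0% response after Week 16 and zero change from baseline from Week 16 onward, fixing 26 of 38 endpoint-by-visit results (24 to 27 across the readings of Week 16). This rests on 5.5.4 governing its own subsection and on the visit schedules in Tables 5.1 and 6.2. Results at Weeks 4 to 12 are unaffected. The consequence is confined to exploratory descriptive output; the primary analysis, the secondary analyses and Type I error control do not change. It should be fixed, because without a stated rule the set's post-rescue efficacy results are either predetermined or not reproducible from the SAP.

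**What to change.** Add to SAP Section 5.5.4.1:

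> *For analyses in the Rescue Analysis Set, ICE 4 is handled by the treatment policy strategy (observed values are used); ICEs 1 to 3 and 6 keep the composite strategy and ICE 5 the treatment policy strategy. Change from baseline is measured from the Week 0 baseline defined in Section 5.1.*

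The second sentence confirms the Section 5.1 default, so that no one substitutes a Week 16 baseline. Using fully observed data for all ICEs would be a defensible alternative; whichever is chosen must be written down, because the numbers differ. If outputs already exist, document the rule that was actually used.

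The cost is two sentences and a programming flag. No new data are needed, and the primary and secondary analyses are untouched.

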5.6. Safety Analyses

Safety data, including but not limited to, AEs and changes in laboratory assessments, will be summarized. Since vital signs and physical examination data were not collected on the eCRF, no summaries will be provided for vital signs and physical examination findings.

All safety analyses will be based on the Safety Analysis Set. In general, participants will be analyzed according to their assigned treatment. However, participants assigned to placebo who incorrectly received guselkumab at any time will be analyzed in the guselkumab group; participants assigned to guselkumab who received only placebo during the study will be analyzed in the placebo group.

For all continuous safety variables, descriptive statistics by intervention group will include the N, mean, standard deviation, median, minimum, and maximum. Categorical variables will be

summarized by intervention group using frequency counts and percentages. No formal statistical analyses are planned.

